### ***Sampling Method***

The sampling methods for this study are the same as those used in our 2002 baseline GPS. The sampling frame for the study will be based on 2005 data on household distribution from the Peruvian INEI. Clusters with an average size of 40 households will be defined by INEI. For each participating city, 108 clusters will be randomly selected.

Field workers will visit all households in the selected clusters, locating households with eligible members. A random sample of 10 households with eligible members will be selected from each cluster (or all households if less than 10).

The interviewers will return to the selected households. If more than one household member meets the inclusion criteria, the person with the most recent birthday will be selected for participation. At this time, an appointment to meet the selected person will be made. Selected participants will then be interviewed to confirm eligibility and to conduct the consent process to determine willingness to participate, and to complete the study procedures. Only in cases when eligibility of the participant could not be confirmed, the eligible person with the next most recent birthday will be selected.

### ***Field Work***

Field work will be divided into 9 periods lasting 10 days each, corresponding to the 9 independent samples selected for each city. Each interviewer has to cover 4 clusters during the first 8 days of each period. Although the ninth day of the period is programmed for visits to participants not found during the initial visit, there is no set limit for the number of appointments made to find selected participants. Recruitment of participants will continue until, at the end of a period, the gender-specific sample size has been reached or exceeded. It is expected that less than 100 clusters will be needed to reach the women's sample size, while in most cities, all 108 clusters will have to be visited to complete the sample size for men. Interviewers will conduct field procedures wearing study gowns and carrying a backpack with survey materials and a small portable cooler containing frozen acrylamide gel bags.

### **3.2 FSW Survey**

For this study, FSW are defined as women who offer their personal sex services at venues of sex work identified in the participating cities. Two hundred FSWs will be enrolled for the study in each of the 20 cities, for a total of 4000 women. The recruitment period will be three months. Enrollment will be carried out in the same cities selected for the GPS.

## **Inclusion Criteria**

FSWs who meet all of the following criteria will be eligible for inclusion in this study:

- Women found offering sex services at selected venues during pre-scheduled visits
- Age fourteen years or older
- Mentally capable of providing informed consent and responding to a questionnaire
- Willing to participate in the survey by providing independent verbal informed consent

Participation in previous surveys, including our own STD surveys, does not preclude participation.

## **Exclusion Criteria**

FSWs unable to provide informed consent because of obvious mental impairment due to the use of alcohol or drugs will not be eligible for this study.

## **Participant Retention and Withdrawal**

No follow-up of participants is required, and therefore no measures for retention are planned. Participants may voluntarily withdraw from the study for any reason at any time.

## **Recruitment Process**

### ***Training and Selection of Field Personnel***

Local field work teams for each city will be composed of three counselors, a laboratory technician and a health promoter, usually a peer FSW. A centralized training workshop will be offered to counselors before the beginning of field activities. In addition to training in selection of study participants and the appropriate completion of the study questionnaire, the workshop will include modules on ethical issues including appropriate consent procedures granting confidentiality and avoiding any form of coercion. Laboratory technicians will receive training on appropriate techniques for sample collection, processing, and shipping, as well as on biosafety.

### ***Sampling Method***

In order to ensure comparability, sampling methods for this survey are similar to those used in our previous FSW survey. Local teams will begin field activities by performing a census of sex work venues (places where FSW meet their potential clients). These venues will be identified by the health promoter and key informants within each city. Team members will record the location and characteristics of the venues, as well as the approximate number of FSWs expected to be found at the venue at different times during an average week. The census will end when all accessible sex work venues have been recorded. Although it is expected that not all sex work venues will be identified by the census, extremely hard to reach venues are likely of low epidemiological importance, as they probably serve small closed circles of clients. At the end of the census, copies of the field work records will be sent to the UPCH in Lima. For cities where more than 200 FSWs were identified by the census, a sample of about 200 women will be selected by the time-location sampling method. For cities where fewer than 200 FSWs are identified, the local team will try to enroll all FSWs identified.

Local teams will visit commercial sex venues and invite all FSWs present in that venue to participate in the study. Sampling collection for this study will be completed in a single visit for all participants.

After providing verbal informed consent, study participants will complete an interviewer-administered questionnaire and undergo HIV and STD counseling and testing. All participants will receive a copy of the informed consent.

Basic demographic data will be collected from the FSWs who are present at the venue during the visit but who do not meet the eligibility criteria or who refuse to participate.

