#### **FSW Survey**

For this study, FSW were defined as women who offer their personal sex services at venues of sex work identified in the participating cities. The goal for each survey included 200 FSW enrolled in each of the cities (24 cities at baseline and 20 cities in outcome surveys), for a total of 4,800 at baseline and 4,000 in 2005 and in 2006. Enrollment was carried out in the same cities selected for the GPS conducted during 2002-03 for the baseline survey and 2005 and 2006 surveys, and according to the same timeline and timeframe as the GPS in the 2005 and 2006 surveys (3 months).

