## POWER CALCULATIONSBB

In Table 2 we present power calculations for testing for a 30-50% reduction in the primary STD outcomes between the treatment and control communities based on the random

---

BB Power calculations taken from “PREVEN trial summary.doc” dated 3/7/06 and presented for DSMB review in April 2006.

population survey of 600 men and women per city. The FSW population is considered separately. These calculations make use of the standard sample size/power formula for matched community randomized trials, as shown below.

$$n = 2 + \frac{(Z_{1-\alpha} + Z_{1-\beta})^2 \left[ p_1(1-p_1)/f + p_2(1-p_2)/f + k^2(p_1^2 + p_2^2) \right]}{(p_1 - p_2)^2}$$

In this formula  $p_1$  and  $p_2$  are the disease prevalences in the treatment and control communities, respectively,  $k$  is the coefficient of variation of disease prevalence between communities,  $f$  is the number of individuals per community and  $n$  is the number of communities. The Z's in the formula represent standard normal quantiles for appropriate type I and type II error rates. Disease prevalence in the control communities and the coefficient of variation are based on the baseline survey data.

Although the investigators cannot be formally blinded to the treatment assignments, only pooled results (over the two study arms) will be presented by the statistician at investigator meetings.

[figure not shown]
**Table 2. Power for comparing treatment ( $n = 10$ ) and control communities ( $n = 10$ ) given number per community, prevalence,  $\alpha = 0.05$  (1-tailed), coefficient of variation = .10 and indicated reduction in disease in treatment cities. Number of GPS results is reduced from 600 to 500 to allow for refusal to provide biologic samples.**

	Number per community			Percent reduction		
	General	FSW	Prev	30	40	50
	population			Percent	Percent	Percent
Any STD	500		.10	.99	.99	.99
		200	.14	.87	.98	.99
Chlamydia	500		.04	.86	.98	.99
Trichomonas	250		.05	.72	.92	.99
Syphilis	500		.01	.41	.63	.81
HIV	500		.005	.27	.40	.57

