### 1.2 FSW & Client Surveys in 2003: Sampling, Participation and Responses

Prostitution is legal in Peru and is regulated by the national government and local authorities. Traditionally, the MINSA (Ministry of Health) anti-venereal disease clinics have offered periodic checkups to FSWs. Starting in 1996, the MINSA established a nationwide system for improved voluntary periodic clinical examination and treatment directed to FSWs, setting up STD reference centers in all the main cities of Peru. The system also included the use of peer educators visiting sex work venues to promote safer behaviors and the use of the clinical services offered by the government. In 1998 the MINSA started a sentinel surveillance system directed to high risk populations, including FSWs. Nationwide surveys of FSWs have been carried out in years 1998, 2000, and 2001. These surveys included mostly FSWs using the services of the STD reference centers. A 2003 survey was conducted in collaboration with the PREVEN study, and was carried out at sex work venues. The sampling method and study procedures are described in greater detail in Sections 3.2 and 4.2, respectively.

During January-March 2003, [name] (a co-investigator for this project), the OGE (Peruvian General Office of Epidemiology), and the regional AIDS and STD Offices undertook surveys of FSW and their clients in the same 24 cities. Our 2003 time-venue baseline survey of FSW and clients achieved 87.1% (range 63% - 100% per city) participation from FSW and 82.8% participation from clients. Of 4494 FSW participants, nearly all responded to sensitive questions, 98.8% provided blood samples, and 97.4% provided vaginal swabs. Of 4504 client participants, 97.7% provided blood and 95% (those able to void) provided urine.

**STD prevalences for FSW and Clients of FSW:** 14.5% of FSWs had chlamydia, 3.5% had gonorrhoea, 7.9% had trichomonas and 3.9% were RPR reactive. Data suggest that approximately 0.25% of participating FSWs had acquired HIV infection within the last year.

Among clients of FSW, 4.0 % had chlamydia and had 0.2% gonorrhoea. RPR reactivity was found in 5.6% of those with and 2.2% of those without recent history of genital ulcer ( $p < .05$ ). Data suggest that approximately 0.25% of the clients acquired HIV infection within the last year.

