## 6. STATISTICAL CONSIDERATIONS

### 6.1 Review of Study Design

This CRT is designed to test a multi-faceted intervention to reduce STDs. It will be conducted in 20 medium sized (> 50,000 people) cities in Peru. Ten cities will be randomized to the intervention and ten cities will serve as controls. The intervention consists of programs to educate pharmacy workers and health care providers, as well as outreach to FSWs. The primary endpoint will be a positive test for gonorrhea and/or chlamydia and/or trichomoniasis, and/or syphilis in a high risk group of FSW and in the lower risk young adult general population, as measured by the surveys described previously. The secondary endpoints that will be evaluated are positive tests for bacterial vaginosis and HIV. The study has power to determine if the intervention can reduce the burden of these STDs in the general population by 30-50% (depending on the STD). Changes of this magnitude have clear implications for public health. Smaller effects, even if present, may not be sufficient to change public health practice and, in any event, would be logistically very difficult to detect.

The surveys described above will be conducted in the 20 cities mentioned above over a period of 3 months. The proposed household based general population survey of men and women 18 to 29 years of age will be used to evaluate the study endpoints. In addition, we will conduct a venue-based survey of FSWs. Cluster sampling will be used for the former, while time-location sampling will be used for the latter survey.

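### Table 2 counts clustered survey results as independent, keeps FSW at the goal of 200 per city, and prints an FSW power that its own inputs do not give

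*Supplement*

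**What the plan says.** The power section of the 2010 Protocol Summary, and section 6.2 of the April 2006 trial summary, use the matched-community formula. Here f is the number of people per community and k is the coefficient of variation between communities. Table 2 takes f = 500 for the GPS (250 for trichomonas) and 200 for FSW, k = .10 throughout, 10 cities per arm and one-tailed alpha .05.

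On how people are sampled, section 6.1 of the trial summary says "Cluster sampling will be used for the former, while time-location sampling will be used for the latter survey". For the GPS, "For each participating city, 108 clusters will be randomly selected". For FSW, "Local teams will visit commercial sex venues and invite all FSWs present in that venue to participate in the study". The 2010 protocol describes both designs in the same way under its sampling methods.

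On numbers, the table note says "Number of GPS results is reduced from 600 to 500 to allow for refusal to provide biologic samples". No such cut is made for FSW. The 2010 protocol says "The goal for each survey included 200 FSW enrolled in each of the cities". The trial summary is firmer: "Two hundred FSWs will be enrolled for the study in each of the 20 cities, for a total of 4000 women". Its sampling rule allows for less: "For cities where fewer than 200 FSWs are identified, the local team will try to enroll all FSWs identified". Section 1.2 reports the baseline result: "Of 4494 FSW participants, nearly all responded to sensitive questions, 98.8% provided blood samples, and 97.4% provided vaginal swabs".

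**The concern.** People living in one small area, or women working at one venue, tend to share risk. The sampling variance of a city prevalence is then DEFF × p(1-p)/f, where the design effect DEFF is usually above 1. The formula has no such term, and k is defined as variation between cities, which is a different component.

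FSW f is also a goal, not an expected yield. Table 2 allows for missing specimens in one survey and not in the other.

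What is at stake is how a null result is read. Section 6.1 of the trial summary says that the study can detect reductions of 30-50%, depending on the infection. The FSW composite and the single infections are formal secondary endpoints, and several have modest stated power.

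**Working it through.** **Formula.** Solved for power, the plan's formula is Φ( √[ (n-2)(p1-p2)² / V ] - 1.645 ), with V = p1(1-p1)/f + p2(1-p2)/f + k²(p1²+p2²), n = 10 and k = .10.

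**Reproducing the GPS rows.** Chlamydia at a 30% reduction compares .04 with .028:
- V = .0000768 + .0000544 + .0000238 = .000155
- √(8 × .012²/.000155) = 2.726, and 2.726 - 1.645 = 1.081, so power is .860 (printed .86).

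At 30% the other GPS rows give composite .990, trichomonas .720, syphilis .415 and HIV .266, against .99, .72, .41 and .27. The 40% and 50% cells also agree, taking .99 as the table's ceiling. So the GPS rows apply a design effect of exactly 1.

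**The FSW row.** This compares .14 with .098 at f = 200:
- V = .000602 + .000442 + .000292 = .001336
- √(8 × .042²/.001336) = 3.250, and 3.250 - 1.645 = 1.605, so power is .946 (printed .87).

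At 40% the formula gives .998 against .98. A two-sided test gives .901 at 30%, which does not match either. The printed .87 would follow from f of about 135, from DEFF of about 1.5 at f = 200, from k of about .165, or from p of about .10. The documents do not say which, if any, was used.

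**FSW with the baseline yield.** 4494/24 = 187 per city, and × .974 with swabs = 182. At f = 182, V = .001439, the ratio is 3.131 and power is .931. Since .87 corresponds to an effective f of about 135, the row is overstated only if DEFF exceeds 182/135 = 1.35 (200/135 = 1.48 at f = 200). The documents give neither a venue ICC nor the number of women per visit. With an assumed ICC of .05 and f = 182:

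| Women per visit (assumed) | DEFF | Power, 30% reduction |
|---|---|---|
| 5 | 1.20 | .90 |
| 10 | 1.45 | .85 |
| 20 | 1.95 | .76 |

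**GPS with clustering.** DEFF = 1 + (m-1) × ICC, where m is results per cluster. At f = 500, m = 500/108 = 4.6, so an ICC of .01 to .05 gives DEFF 1.04 to 1.18. The baseline yield from sections 1.1 and 1.1's participation figures is 15,492 × .86/24 = 555 results per city, so m = 5.1. The trichomonas row uses half of f and half of m. Power at a 30% reduction:

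| Row | Printed | f = 500, ICC .01 | f = 500, ICC .05 | f = 555, ICC .01 | f = 555, ICC .05 |
|---|---|---|---|---|---|
| Composite | .99 | .988 | .982 | .992 | .986 |
| Chlamydia | .86 | .851 | .814 | .876 | .838 |
| Syphilis | .41 | .406 | .373 | .432 | .393 |
| Trichomonas | .72 | .716 | .699 | .750 | .730 |

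Syphilis at a 50% reduction (printed .81) is .80 to .76 at f = 500.

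**Break-even for chlamydia at f = 555.** Printed power holds while f/DEFF is at least 500, so DEFF may reach 555/500 = 1.11. The ICC may then reach .11/4.14 = .027.

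**What k can contain.** Binomial noise alone gives a coefficient of variation of √(.90/(.10 × 500)) = .134 at p = .10. So k = .10 is hard to read as the raw variation of sampled city prevalences. If only binomial variance was removed, k already holds part of the cluster effect.

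**The case against.** A reader might infer that all the stated powers are too high. The documents do not support that.

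- **FSW.** The only correction that rests on documented figures, f = 182, gives .931, which is above the printed .87. The table's prevalence may also be low: baseline chlamydia alone was 14.5%, and a composite cannot be below one of its components. At an assumed .20, f = 182 and DEFF 1.95 still give .88.
- **GPS.** If baseline yield is used for FSW it must be used for the GPS too, and 555 exceeds 500. This offsets an ICC up to about .027. The offset depends on recruiting beyond target, as baseline did (15,492/24 = 645 per city). At exactly 600, 86% gives 516 results, and the break-even ICC falls to (516/500 - 1)/(516/108 - 1) = .008.
- **k.** Its derivation is not stated, so it may carry some within-city clustering.

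A reader might also infer that the rule cannot give 200 women per city and that the total will be about 3,750. That goes too far. The protocol calls 200 a goal, and the baseline mean comes from 24 cities, four of them outside the trial. The minimum age was later lowered to 14, and mobile teams screened 2,285 women in one cycle across the ten intervention cities. Enrolling nearly everyone in a small city also reduces sampling error.

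These points stand. They limit the size and direction of the effect. They do not supply the missing design effect, justify leaving FSW uncut for specimens, or explain the FSW row.

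**Conclusion.** Three faults hold in the current protocol. Table 2 has no design effect and does not say whether k includes one. FSW f is the goal, where baseline gave 187 per city, or 182 with swabs. The FSW row does not follow from its inputs (.946 against .87).

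The direction of error is not uniform. The FSW cell at 30% is below what its inputs give, and is too high only with a design effect above about 1.35 at f = 182. At f = 500, the GPS losses for ICC up to .05 are at most about 5 points on single infections, and the primary composite stays at .98 or above. At the baseline yield, the lower half of that ICC range produces no overstatement for chlamydia. Every loss from clustering rests on an assumed ICC.

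This is a planning-power fault, not a validity fault. The primary analysis compares city prevalences, so within-city clustering is carried in its residual variance.

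**What to change.** - Recompute Table 2 with p(1-p)/f multiplied by design effects estimated from the baseline data, using the household cluster code for the GPS and the venue code for FSW. If k already includes this component, state how it was estimated instead.
- Use expected numbers with specimens for both surveys. Baseline gives about 555 per city for the GPS and 182 for FSW; say how far the outcome surveys are expected to match these. Describe 200 FSW as a goal in every place, without fixing a lower total.
- Correct the FSW row, or state the inputs that produce .87.
- Restate the FSW and single-infection powers.

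The cost is a recalculation from data already held and a corrected table. It needs no extra participants and no change to the analysis.

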## **4. STUDY PROCEDURES – 2005 OUTCOME SURVEYS**

### **4.1 General Population Survey**

#### **Interview**

Participants will respond to a face-to-face questionnaire administered by the interviewer using a hand-held computer. Although the questionnaires to be used are roughly the same as the ones used in our 2002 surveys, a section on reproductive health has been added, and a few other minor changes have been introduced. The format of the questionnaire for the proposed survey will have to be adapted to

the hand-held computer, and pilot tested in the field. We believe that none of these changes will jeopardize the comparability of the two surveys.

The interviewer will demonstrate the use of the hand-held computer while administering the questionnaire. The questionnaire will collect data on demographic and household characteristics, travel, migration, labor, health seeking behavior, marriage, contraception, knowledge about STDs and reproductive health. Afterwards, the participants will respond to a self-administered questionnaire on the same hand-held computer, exploring characteristics of the participant's sexual behavior. This questionnaire will be completed privately by the participant. The computer program will restrict access to the responses given by the participants to the self-administered portion of the questionnaire.

### **Biological Sample Collection**

After completing the questionnaires, the interviewers will explain the procedures for sample collection. Men will be asked to provide urine (about 15 ml) for STD tests in a 50-ml plastic container. Females will receive a rack with 1 polyester/plastic stick vaginal swab and two cotton/wooden stick vaginal swabs, which will be self-applied in that order by the participant. Then the interviewer will place the polyester swab in a 2 ml cryovial. The first cotton swab will be used to inoculate an InPouch TV® culture for *T. vaginalis* in the field. The second cotton swab will be used to prepare a vaginal smear in a glass slide in the field. Females unwilling to provide self-applied vaginal swabs will be asked to provide urine samples.

After collection of urine or vaginal samples the interviewers will collect venous blood samples from men and women using a vacuum extraction system. Syringes will be used when extraction of blood with the vacuum system is difficult.

Participants providing biological samples will receive a booklet with information about HIV and the HIV tests as pre-test counseling for HIV and a referral card to be used at a local health center to receive STD/HIV counseling and claim test results.

Urine samples, polyester swabs, and blood samples will be placed inside the cooler for transportation to the local specimen processing and transport laboratory facilities (SPTLF). *T. vaginalis* cultures and glass smears will be transported to the laboratory inside the backpack.

Consent forms, referral cards and samples will be labeled using preprinted self-adhesive labels with alphanumeric codes and barcodes. The same code will be entered into the hand-held computer.

